4.1 Objectives

The objective of this study is to demonstrate the feasibility and safety of the NOVIS Transcarotid NPS when used for the transcarotid intervention of patients that have failed transfemoral endovascular therapy in the case of anterior circulation strokes due to large vessel embolic occlusions.

5 Device Overview

5.1 Device Description

The NOVIS Transcarotid Neuroprotection System (NPS)

The NOVIS Transcarotid Neuroprotection System is a modified version of the ENROUTE NPS. The NOVIS Transcarotid NPS consists of four primary components:

- Transcarotid Arterial Sheath with Arterial Dilator
- Venous Return Sheath with Venous Dilator
- Flow Controller with Filter
- 0.035" Extra Support, J-Tip Guidewire

When assembled, the NOVIS Transcarotid NPS creates an arteriovenous shunt that can reverse the flow of blood in the carotid artery from antegrade to retrograde, shunting embolic particles away from the cerebral circulation during endovascular interventions (see Figure 1 below). The NOVIS NPS is intended to provide vascular access and embolic protection during treatment with neurothrombectomy devices; it is not intended to aspirate the carotid artery and its branches or to perform mechanical neurothrombectomy at a distance from the site of occlusion.

[figure not shown]

Figure 1. NOVIS Transcarotid Neuroprotection System

Key dimensions of the NOVIS Transcarotid NPS are listed in Table 3 and include lengths and diameters of each component.

Table 3. Key Dimensions of the NOVIS Transcarotid Neuroprotection System

Attribute	Transcarotid Arterial Sheath	Venous Return Sheath	Arteriovenous Shunt**
Working Length	11 cm (4.3 in)	11 cm (4.3 in)	
Total Length	33.2 cm (13.1 in)	13.6 cm (5.4 in)	102 cm (40.2 in)
Inner Diameter	Sheath Tip ID: 8 Fr (2.7 mm/0.105 in)	Sheath Tip ID: 8 Fr (2.7 mm/0.105 in)	
Outer Diameter	10.5 Fr	10.5 Fr	

Attribute	Transcarotid Arterial Sheath	Venous Return Sheath	Arteriovenous Shunt**
	(3.5 mm/ 0.136 in)	(3.5 mm/ 0.136 in)	

** The Arteriovenous Shunt total length includes the large diameter tubing from the Arterial Sheath to the Venous Return Sheath.

Each component of the NOVIS Transcarotid NPS is described in the following sections.

5.2 Transcarotid Arterial Sheath

The NOVIS Transcarotid Arterial Sheath with Uber-Flex™ Tip consists of an 8 Fr. Arterial Sheath and an Arterial Dilator (see Figure 2). The Transcarotid Arterial Sheath permits access to the common carotid artery (CCA), and includes the following features:

- A radiopaque tip which allows visualization of the sheath tip under fluoroscopy.
- Printed centimeter markers to measure sheath insertion depth.
- An extension tube which extends the proximal end of the Arterial Sheath away from the radiation field.
- A female luer connection on the proximal end of the extension tube for the attachment of a Rotating Hemostasis Valve (RHV). The RHV (not included) will provide hemostasis after Dilator removal, allow introduction of interventional devices into the Arterial Sheath and enable continuous heparinized saline flush.
- Suture Eyelets for securement of the Arterial Sheath.
- An Arterial Stopcock which connects the Arterial Sheath to the Flow Controller via a “quick connect” type fitting. The handle on the Arterial Stopcock is used to shunt flow once the Arterial Sheath is connected to the Flow Controller.

[figure not shown]

Figure 2. NOVIS Transcarotid Arterial Sheath and Dilator

5.3 Venous Return Sheath

The NOVIS Venous Return Sheath consists of an 8 Fr. Venous Sheath and a Venous Dilator (see Figure 3). The Venous Return Sheath is used to gain femoral vein access, and includes the following features:

- A radiopaque tip which allows visualization of the sheath tip under fluoroscopy.
- A Hemostasis Valve on the proximal end of the Sheath to provide hemostasis after removal of the Dilator.
- Suture Eyelets for securement of the Venous Return Sheath.
- A Venous Flow Line and Stopcock which connects the Venous Return Sheath to the Flow Controller via a “quick connect” type fitting. The Venous Stopcock also permits saline prep, saline and contrast injections, and aspiration.

[figure not shown]

Figure 3. NOVIS Venous Return Sheath

5.3.1 Flow Controller

The NOVIS Flow Controller (see Figure 4) connects the Transcarotid Arterial Sheath to the Venous Return Sheath and includes the following features:

- A Flow Controller which regulates the rate of reverse flow via the High/Low Switch and which allows temporary shut off of the Controller/Filter Line during contrast injections via the Flow “Stop” Button (detail in Figure 5). Pressing the switch towards “Low” sets the flow setting to low flow and pressing the switch towards “High” sets the flow setting to high flow.
- An in-line Filter which captures embolic debris from the blood flow through the shunt.
- An in-line Check Valve which prevents inadvertent flow or injection of blood or fluid through the shunt in the arterial direction.
- “Quick-Connect” type connections to the Transcarotid Arterial Sheath and Venous Return Sheath.
- A “Pull to Prep” Toggle Loop that is removed and discarded prior to system prep and usage.

[figure not shown]

Figure 4. NOVIS Flow Controller

Figure 5. Flow Controller Detail

The Flow Controller has two functions. The first is to enable the user to switch between Low and High flow modes via the use of the High/Low switch to modulate reverse flow. This is accomplished by providing two parallel flow paths through the Controller Line: one with a low resistance flow path and the other with a high resistance flow path. When the switch is on Low, the low resistance flow path is pinched off, requiring all the blood flow to go through the high resistance path. When the switch is set to High, both paths are open and the blood flows through both paths in parallel, which in combination form a low resistance flow path.

The second function of the Flow Controller is to momentarily block the flow of blood through the Controller Line via a Flow Stop Button. This button is spring-loaded to be normally open and is designed to be used during injection of contrast through the arterial sheath into the carotid vasculature. By shutting off the arteriovenous shunt flow line during contrast injection, the contrast solution is prevented from immediately filling the shunt line rather than entering the artery. The normally open configuration of the button prevents the user from neglecting to re-open the shunt line (and thereby re-establishing reverse flow) after a contrast injection.

5.4 Intended Use

The NOVIS Transcarotid Neuroprotection System (NPS) is intended to provide transcarotid vascular access and embolic protection for the introduction of diagnostic agents and therapeutic devices during treatment of acute ischemic stroke (large vessel occlusion in the anterior circulation) in patients with distal ICA, MCA M1, proximal MCA M2, single-vessel MCA M2, dominant MCA M2, or co-dominant MCA M2 occlusions, within 24 hours of time last known well. Appropriate patients will have undergone a failed transfemoral attempt (as defined in Appendix 4) and have appropriate anatomy described below:

- Adequate femoral venous access as assessed by ultrasound
- Common carotid artery reference diameter of at least 6 mm

The NOVIS Transcarotid Neuroprotection System (NPS) is contraindicated for use in patients with significant disease of the ipsilateral common carotid artery.

The benefits and risks of carotid stenting in AIS patients have not been investigated, thus carotid stenting is not allowed in the NITE 1 Study.

6 Study Design

The NITE 1 Study is a prospective, single arm, multi-center feasibility study for the treatment of patients experiencing an acute ischemic anterior circulation stroke due to large vessel embolic occlusions of the intracranial ICA, MCA M1, proximal MCA M2, single-vessel MCA M2, dominant MCA M2, or co-dominant MCA M2 segments using the open-surgical transcarotid approach. The NOVIS Transcarotid NPS will be used to facilitate the transcarotid approach in patients that have failed transfemoral therapy.

7 Outcomes

7.1 Primary Outcomes

The following primary endpoints will be collected and evaluated in all enrolled patients:

- Device-related Serious Adverse Events – vascular complications including dissection, pseudoaneurysm, hematoma, arteriovenous fistula, thrombus formation, embolization and any vascular complication that may be attributed to the device AND requires surgical repair, surgical wound revision, transfusion, etc.
- Other Serious Adverse Events – permanent cranial nerve injury, new symptomatic ipsilateral hemorrhage and dissections related to ancillary devices
- Functional independence at 90 days (proportion with mRS score 0-2)

7.2 Secondary Outcomes

The following secondary outcomes will be collected and evaluated in all enrolled patients:

- Carotid access time
 - Hospital arrival to neck incision
 - Neck incision to carotid exposure
 - Neck incision to carotid artery catheterization (includes securing of sheath)
 - Neck incision to femoral venous sheath access (includes securing of sheath)
 - Neck incision to initiation of reverse flow
- Time to final revascularization
 - Hospital arrival to OR
 - Last known well to final revascularization
 - Admission to final revascularization
 - OR to final revascularization
 - Cutdown to final revascularization
 - Arterial introduction of interventional tools to final revascularization
 - Total reverse flow time (CCA clamp to CCA unclamp)

- Device-related complications
- Neurologic assessment at 90 days (proportion of patients with a nondisabling or disabling stroke according to NIHSS)
- Technical success rate – Successful introduction of endovascular tools through the NOVIS Transcarotid NPS.
- Rates of revascularization success assessed by angiographic core lab (mTICI \geq 2b)

8 Study Population

8.1 Selection of Patients

Prospective study patients' medical history will be reviewed for potential eligibility by an approved member of the site clinical research team. Once eligibility is established, the research team should review the study follow-up requirements with the patient or patient's legal authorized representative. Patients who will not be able to return to the study site for the required follow-up visits should not be considered for enrollment.

8.2 Patient Eligibility

Patients enrolled into this study will be comprised of male and female patients who have had an acute ischemic anterior circulation stroke due to large vessel embolic occlusion who are candidates for endovascular therapy and in whom transfemoral therapy has failed.

Patients must meet ALL the inclusion criteria to be considered for the study. If ANY of the exclusion criteria are met, the patient cannot be enrolled in this study.

8.3 Inclusion Criteria

1. Patients presenting with acute ischemic stroke of the anterior circulation with large vessel occlusions who are eligible for revascularization using endovascular therapies (stentriever and/or aspiration devices)
2. Occlusion of the intracranial ICA, MCA M1, proximal MCA M2, single-vessel MCA M2, dominant MCA M2, or co-dominant MCA M2 segments
3. Patient has failed transfemoral therapy (see Appendix 4 for definition), and at least 15 minutes have elapsed from groin puncture
4. Patient must meet current NOVIS Transcarotid Neuroprotection labeling requirements
 - a. Adequate femoral venous access as assessed by ultrasound
 - b. CCA reference diameter of at least 6 mm
5. Patient is \geq 18 years of age
6. Patient willing/able to return for protocol required follow up visits
7. Patient or patient's Legally Authorized Representative (LAR) has signed the study Informed Consent form
8. Imaging requirement for patients presenting within 6 to 24 hours from last known well:
 - a. < 1/3 MCA territory involvement, as evidenced by CT
 - b. Clinical Imaging Mismatch defined as one of the following on CTP:
 - i. 0-20 cc core infarct and NIHSS \geq 10 (and age \geq 80 years old)
 - ii. 0-30 cc core infarct and NIHSS \geq 10 (and age < 80 years old)
 - iii. 31 cc to \leq 50 cc core infarct and NIHSS \geq 20 (and age < 80 years old)

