8.4 Exclusion Criteria

Each potential patient must be screened to ensure they do not meet any of the following exclusion criteria. This screening is based on known medical history and data available at the time of eligibility determination and enrollment.

1. Significant disease of the ipsilateral common carotid artery on routine CTA
2. Presence of a cervical ICA loop or other high-risk anatomical features of the ICA on routine CTA, that may preclude the use of the NOVIS NPS
3. Any active or recent hemorrhage within the past 30 days
4. Embolectomy contraindications
 - a. Pre-stroke mRS ≥ 2
 - b. NIHSS ≤ 5
 - c. ASPECTS ≤ 5
5. IV tPA has been or is being administered
6. Last known well > 24 hours ago
7. Known history of severe head injury within past 90 days with residual neurological deficit, as determined by medical history
8. Patient has an isolated hemisphere, defined as intracranial circulation that is fed only by the ipsilateral internal carotid artery and may be detected on prior CTA
9. Known history of neurological or psychiatric disease that would confound the neurological or functional evaluations, e.g., dementia with prescribed anti-cholinesterase inhibitor (e.g., Aricept)
10. Presumed septic embolus, suspicion of bacterial endocarditis or cerebral vasculitis
11. Known history of ipsilateral severe intracranial atherosclerotic disease ($\geq 70\%$ stenosis) documented on prior imaging
12. Patient is known to have an active COVID-19 infection
13. Female who is pregnant or lactating at time of admission
14. Current participation in another investigational drug or device study.
15. Evidence of any other disease or condition expected to compromise survival or ability to complete the endovascular procedure or follow-up assessments during the 90-day follow-up period (e.g. methamphetamine, cocaine, or other recreational drug use)
16. Patient has recurrent or metastatic malignancy or cancer
17. Known history of hemorrhagic diathesis or coagulation factor deficiency
18. Known risks for paradoxical embolism, including intracardiac right-to left shunt (e.g., PFO, ASD, VSD) or history of pulmonary embolism or deep vein thrombosis
19. Patients that have undergone a transradial or transbrachial mechanical thrombectomy attempt prior to enrollment

9 Patient Enrollment

A patient is considered enrolled after:

- 1) written informed consent is obtained,
- 2) meeting all inclusion and none of the exclusion criteria,
- 3) failed transfemoral therapy

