10.3.2 Failed Transfemoral Therapy

For the purposes of this study, failed transfemoral therapy is defined as either a unsuccessful transfemoral mechanical thrombectomy attempt made for at least 15 minutes having elapsed from groin puncture or inadequate or prohibitive anatomy deems a transfemoral approach not possible, as determined by the operator (see Appendix 4 for definition).

Reasons for failed transfemoral therapy should be documented both on the patient's medical record and study CRFs.

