23.6 Minimization of Risks

In order to mitigate the risks to the patient outlined above in Section 23.2 – 23.4, a variety of measures have been implemented into the study design to ensure patient safety.

The Sponsor will ensure that all Investigators will meet pre-specified criteria for Investigator selection and will successfully complete the mandatory device and protocol training provided by the Sponsor. All Investigators and Sites selected for this study have sufficient expertise and resources to manage any adverse events and conduct endovascular procedures. The Sites selected for the study are certified Comprehensive Stroke Centers to ensure necessary staff knowledge and appropriate equipment and resources. Participating investigators must be neurosurgeons who are also “TCAR trained”, which is a training and credentialing status that meets the requirements of the Society for Vascular Surgery (SVS) and represents the operator’s knowledge of performing the TCAR procedure using the ENROUTE NPS System, which is the predecessor to the NOVIS NPS. Additionally, the investigators must currently perform or have hospital privileges to perform CEA at the investigational site in the case that emergent surgical repair of the carotid artery becomes necessary.

The sample size of the study has been limited in size and to patients who have a failed transfemoral attempt, leaving no other thrombectomy therapy options other than the study procedure.

Sites must obtain IRB approval prior to screening and enrolling patients into the study. Signed Informed Consent will be required prior to participation, which will explain their treatment choices

and the risks and benefits of being in the study. CTP neurological imaging maps will be used to measure the core infarct volume and only those subjects who have small to moderate core infarct volumes will be enrolled into the trial. Sites will be provided with Instructions for Use for the NOVIS NPS being used. During the procedure the Investigators will pre-place sutures at the planned common carotid artery puncture site to provide rapid hemostasis upon arterial sheath retrieval, as outlined in the Instructions for Use. The artery and incision will be closed using standard surgical techniques and will be monitored post-operatively.

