The Site will observe standard hospital procedures in the care of patients who undergo endovascular procedures. Frequent neurological and hemodynamic checks will be performed per standard hospital procedures during and post-procedure. Vital signs, particularly the patient's heart rate and blood pressure during and after the procedure will be monitored as standard of care, since rapid intervention must be undertaken to correct sudden changes in the patient's hemodynamic or neurologic status.

As part of this study protocol, the Investigator ensures all patients meet all enrollment criteria listed in Section 8 with particular adherence being made to ensure that the patient population consists of those that have undergone a failed transfemoral attempt (see Appendix 4 for definition).

Additional follow-up assessments at 30- and 90-day intervals are predesigned into the study to aid in monitoring patient safety and assessing any change in the patient's outcomes. The investigator will ensure the patient remains compliant with follow-up instructions and visits. The patients and their families will also receive the research teams contact information in case of an emergency or occurrence of an adverse event.

Safety monitoring of the data, consisting of individual event and aggregate data review, will be ongoing and conducted at a rate commensurate with patient enrollment in the trial. The DSMB will provide subject safety oversight and make recommendations to Sponsor regarding continuing enrollment, modifying, or stopping the study early based upon a review of the comparative rates of SAEs.

As a result of these risk mitigations, this study has been designed to demonstrate the potential benefits of the NOVIS Transcarotid NPS in the treatment of acute ischemic stroke caused by large vessel occlusions.

24 Non-Protocol Research

The Sponsor has a legal responsibility to the regulatory authorities to fully report all the results of sponsored clinical studies. No investigative procedures other than those in this protocol shall be undertaken on the enrolled patients without the PRIOR written approval of the reviewing IRB and the Sponsor.

25 Use of Information and Publication

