Appendix 4. Definitions

Access Site Complication

Complication related to the vascular access site for the index procedure including but not limited to dissection, pseudoaneurysm, hematoma, arteriovenous fistula, thrombus formation, embolization and any vascular complication that may be attributed to the device AND that requires surgical repair, surgical wound revision, transfusion etc.

Adverse Event (AE)

Any unintended disease or injury or untoward clinical sign in a research patient.

CEA—Carotid Endarterectomy

A surgical procedure in which atherosclerotic plaque is removed from the diseased carotid artery.

CVA—Cerebral Vascular Accident (See definition for Stroke)

Death

Cessation of brain, cardiac, and pulmonary functions

Neurologic Death Death due to stroke or other neurologic cause.

Cardiac Death Death due to MI or other cardiac cause.

Other Death that cannot be attributed to neurologic or cardiac causes.

Device Malfunction

The failure of a device to meet any of its performance specifications or perform as intended. Performance specifications include all claims made in the labeling of the device.

Device Related Adverse Event

An Adverse Event that was directly caused by the study device (NOVIS NPS).

Distal Embolization (DE)

Embolization of pieces of the original thrombus “downstream” in the same vascular territory as the original thrombus.

Embolization to New Territory (ENT)

Any new infarct seen in the ipsilateral ACA for MCA occlusions, on CTA or MRI at the 24-hour time point compared to baseline CT or MRI.

Failed Transfemoral Therapy

Either a transfemoral mechanical thrombectomy attempt was made unsuccessfully with at least 15 minutes having elapsed from groin puncture, or there is inadequate or prohibitive anatomy deeming a transfemoral approach not possible, as determined by the operator.

Good Clinical Outcome

A measure of neurologic functional outcome with a score of 0–2 on the modified Rankin Scale (mRS), assessed at the 90-day follow-up visit.

Intracranial Hemorrhage

A hemorrhage, or bleeding within the skull

Isolated Hemisphere

Intracranial circulation that is fed only by the ipsilateral internal carotid artery and may be detected on prior CTA/MRA

Neurological Deterioration/Worsening

A 4 or more-point increase in NIHSS from baseline to discharge. Neurological worsening could be new or evolution/progression of the index stroke.

Permanent Cranial Nerve Palsy or Injury

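### Inclusion 3 applies a 15-minute groin-puncture condition to every patient, but the Appendix 4 definition it cites accepts prohibitive anatomy without one

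*Protocol*

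**What the plan says.** The third inclusion criterion (Protocol section 8.3) is "Patient has failed transfemoral therapy (see Appendix 4 for definition), and at least 15 minutes have elapsed from groin puncture". Section 8.2 makes the criteria cumulative: "Patients must meet ALL the inclusion criteria to be considered for the study". Section 9 makes "meeting all inclusion and none of the exclusion criteria" a condition of enrollment and lists failed transfemoral therapy beside it as a separate condition.

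The Appendix 4 definition has two branches. The first is an unsuccessful thrombectomy attempt with 15 minutes gone since groin puncture. The second is "or there is inadequate or prohibitive anatomy deeming a transfemoral approach not possible, as determined by the operator". Section 10.3.2, the procedural text, has the same two branches, the second worded as "inadequate or prohibitive anatomy deems a transfemoral approach not possible, as determined by the operator".

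Other sections point both ways. Section 23.6 describes the sample as "limited in size and to patients who have a failed transfemoral attempt, leaving no other thrombectomy therapy options other than the study procedure", with no reference to Appendix 4. Section 5.4 and a later sentence in 23.6 also speak of an attempt, but both send the reader to Appendix 4 for its meaning.

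On analysis sets, Protocol section 14.1 and SAP section 4 restrict ITT to consented patients who satisfy every eligibility criterion and have failed transfemoral therapy. PP is drawn from ITT. The primary and secondary endpoints are analyzed on those two sets, and SAP section 2 takes its complete NOVIS population from ITT.

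**The concern.** The criterion cites a definition and then adds a condition that part of the definition does not carry. An operator working from section 10.3.2 or Appendix 4 may conclude that a patient with prohibitive anatomy qualifies without a puncture. An operator working from section 8.3 must turn the same patient away, or puncture and let 15 minutes pass. Sites acting in good faith could then take different patients to open carotid access with an investigational device. Section 23.6 presents the failed-attempt restriction as a risk mitigation, so its scope should be beyond doubt.

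The disputed patients are ones the protocol itself describes. Section 3.1 says that peripheral vascular disease can rule out femoral access. Section 10.2.1 requires head and neck CT angiography before the procedure, so anatomy may be known before any puncture. Section 3.2 cites a direct carotid puncture series in which some cases were chosen at the operator's discretion after review of that imaging.

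The second matter is what happens to the data of any patient who receives the device and is later found to have breached a criterion. In a feasibility and safety study, those outcomes belong in the primary results.

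**Working it through.** No figure in the plan bears on this, so the check is logical.

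**Eligibility.** Let U be an unsuccessful transfemoral attempt, T at least 15 minutes since groin puncture, and B operator-judged prohibitive anatomy.

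- Appendix 4 and section 10.3.2: (U and T) or B.
- Inclusion 3: [(U and T) or B] and T, which reduces to (U or B) and T.
- Accepted by Appendix 4 but not by Inclusion 3: B without T. These patients have prohibitive anatomy and either no puncture or a puncture less than 15 minutes ago.
- Accepted by Inclusion 3 but not by Appendix 4: none.

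The conflict is therefore one-way and confined to the anatomy branch. Both texts accept an unsuccessful attempt once 15 minutes have passed, and both accept prohibitive anatomy once 15 minutes have passed since puncture.

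**Check of the two remedies.**

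- Option A puts T on both branches of the definition. Appendix 4 becomes (U or B) and T, which is exactly what Inclusion 3 admits now.
- Option B applies T in Inclusion 3 only to patients who qualify through an attempt. Inclusion 3 becomes (U and T) or B, which is Appendix 4 as it stands. It adds the B-without-T patients.

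**Analysis sets.** This step does not use the conflict above.

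1. ITT requires every eligibility criterion to be met, so a treated patient found to have breached one is not in ITT.
2. PP is a subset of ITT, so that patient is not in PP.
3. The NOVIS comparison population in SAP section 2 is the ITT population, so the patient is not there either.
4. Protocol section 7.1 collects primary endpoints in all enrolled patients, but section 9 makes eligibility part of being enrolled, so it does not restore the patient.
5. Section 10.3.3 follows adverse events seen after reverse flow through study exit, but assigns the patient to no analysis set.

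For scale, one patient in a set of 30 (the PP minimum) carries 1/30 = 3.3 percentage points of a proportion. In a set of 60 (the ITT maximum) it is 1/60 = 1.7 points. These show the weight of one patient and do not estimate how many would be lost.

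**The case against.** The strongest reply on eligibility is that the trailing clause of Inclusion 3 is shorthand for the first branch of the definition and was never meant to override the second. The criterion does refer to Appendix 4, and section 10.3.2 gives the two-branch rule as the study's working definition. This is a fair account of possible intent. It does not remove the conflict, because the clause is joined with a plain conjunction, carries no exception for anatomy, and sits in a list where every item is mandatory. What stands is that intent is unclear. A reader might infer that Inclusion 3 simply governs and that anatomy-only patients are ineligible beyond argument. Sections 8.2 and 9 favor that reading, but a criterion that itself defers to Appendix 4 cannot settle it alone. The patient flow diagram, which is not shown in the text available, might.

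Existing controls also limit the harm. Reasons for transfemoral failure go into the medical record and the CRF (10.3.2), so anatomy-only cases can be identified. Investigators are trained on the protocol (18.2), compliance is monitored (19), and no hypothesis is tested (14.3). These help to detect a divergent reading. They do not tell a site which text to follow.

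On analysis sets, SAP section 8 uses all study subjects as the safety denominator, which could be read to include treated ineligible patients. Protocol section 22 does not list an eligibility breach among its major deviations, so a reader might suppose that such a patient stays in PP. Neither rescues the patient. The SAP does not define the subjects it counts, and PP membership first requires ITT membership.

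**Conclusion.** The conflict is real, is in the current text, and should be fixed. It affects patients with operator-judged prohibitive anatomy who have had no groin puncture, or one less than 15 minutes earlier. It rests only on the wording of section 8.3, Appendix 4 and section 10.3.2.

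Its size in patients is unknown. The documents give no expected share of anatomy-only cases. The 5.4% catheterization failure rate cited in section 3.1 comes from a general series of endovascular stroke patients and is not that share. A tally of hypothetical patient types would not help, since it depends on how the types are divided. A reader might also infer that the results will be biased, or that ineligible patients have been treated. The documents support neither claim.

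The analysis-set gap holds on the written definitions for a breach of any criterion. It should not be read as a consequence of Inclusion 3.

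**What to change.** Decide which rule is meant, then make the texts agree.

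- **Option A, if puncture and 15 minutes are required of everyone.** In Appendix 4 and section 10.3.2, define failure as an unsuccessful attempt or operator-determined prohibitive anatomy, in either case with at least 15 minutes since groin puncture. This keeps exactly the group that Inclusion 3 admits now. The cost is wording.
- **Option B, if anatomy alone is meant to qualify.** In Inclusion 3, limit the 15-minute clause to patients who qualify through an unsuccessful attempt, worded so that a patient found to have prohibitive anatomy soon after puncture is also covered. This widens eligibility and needs a revised risk rationale in section 23.6.

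Under either option, align the references to a failed attempt in section 5.4 and in both places in section 23.6. Both options go through the amendment process in section 21. Option B changes patient care, so it needs IRB approval.

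Separately, add one sentence to Protocol section 14.1 and one to SAP section 4: every consented patient in whom NOVIS access is started is followed to 90 days and kept in the ITT and safety analyses, even if later found ineligible. The small downside is that a few ineligible patients are followed and included.
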